## 6.7 Hypothesis

That treatment with rosuvastatin 20mg daily will delay progression of atherosclerosis and reduce biomarkers of activation and inflammation in HIV positive people with intermediate FRS.

## 7 Study objectives

### 7.1 Primary Objective

The primary objective is to determine the effect of rosuvastatin on atherosclerosis progression in individuals with HIV infection who are at moderate cardiovascular risk.

The primary outcome measure will be the difference in cIMT progression (measured as a change from baseline) between the rosuvastatin and placebo arms.

### 7.2 Secondary Objectives

Secondary objectives are to determine in HIV positive patients:

1. The safety profile of rosuvastatin
2. The effect of rosuvastatin on vessel wall function and biomarkers of atherosclerosis and innate immune activation
3. The effect of rosuvastatin on fasting lipids and glucose
4. Whether baseline measures of immune activation and inflammation predicts cIMT or progression of cIMT
5. Whether a change in measures of immune activation and inflammation from baseline after three months of rosuvastatin therapy predicts progression of cIMT

Secondary outcome measures include:

[figure not shown]
1. The rate of adverse effects (symptomatic and biochemical) between the two treatment arms
2. The effect of rosuvastatin on cIMT and cPWV
3. The effect of rosuvastatin on immunological and inflammatory markers (including sCD14, sCD163, neopterin, S-VCAM-1, adiponectin, CCL2, inflammatory (CD16+) monocyte expression of CD38, CX3CR1 and CD11b)
4. The effect of rosuvastatin on fasting total cholesterol, LDL, HDL, TG and glucose levels after 6, 12 and 24 months of therapy
5. The relationship between baseline measures of sCD14, sCD163, and neopterin and baseline cIMT
6. The relationship between baseline measures of sCD14, sCD163, and neopterin and rate of progression of cIMT
7. The relationship between change from baseline to 3 months in markers of immune activation and inflammation (sCD14, CCL2, and inflammatory (CD16+) monocyte phenotypic expression of CD38, CD11b) and progression of cIMT at 12 and 24 months.

## 8 Study Design

### 8.1 Design

The study will be a randomized, double blinded, placebo controlled, multicentre trial comparing the effect of rosuvastatin 20 mg daily versus placebo over 96 weeks in people with HIV infection at moderate cardiovascular risk.

Individuals (n=102) with moderate CVD risk, as estimated by the FRS (10-15% 10 year risk of CVD), who do not qualify for statin therapy under Australian guidelines, will be randomized 1:1 to active rosuvastatin 20mg once daily or matching placebo.

Placebo and rosuvastatin capsules identical in shape and colour will be used to help preserve blinding. Participants on a protease inhibitor based cART regimen will receive 10 mg rosuvastatin or matching placebo.

#### Randomisation

A computerized random number generator will be used to assign treatment arms. Block Randomisation will be stratified by country.

There will be seven study visits over the 96 week duration of the study.

cIMT, cPWV and biomarkers of immune activation and inflammation will be

measured at screening visit and compared to values obtained after 48 and 96 weeks of treatment with the study medication.

cIMT and cPWV measurements will be performed in duplicate, by the same operator at the AH Heart Centre or the Swiss site, who will remain blinded to participant randomization, throughout the study.

All samples will be processed on site at the AH or the Swiss site. Standard laboratory assessments (i.e. biochemistry, full blood examination (FBE), fasting lipids, hsCRP) will be processed by AH pathology department or the Swiss sites' local laboratories. Markers of innate immunity and inflammation will be performed in the Burnet laboratories. Plasma and PBMCs will be separated from research bloods samples, frozen to -140°C and stored onsite in the Burnet laboratory for possible further analysis in the future.

*For Switzerland: Plasma samples for testing of inflammation markers will be stored on site at minus 80° and shipped to central biobank (sérothèque) HUG for analysis at the HUG cardiology laboratory.*

## 8.2 Duration

Ninety-six (96) weeks per patient

Expected duration for entire project – 5 years

## 8.3 Study centres

Patients will be recruited and followed at the Alfred Hospital (Victorian HIV service) Infectious Diseases Clinic.

*Switzerland: Patients will be recruited within the HIV Cohort Network, at the following hospitals following regulatory approval: University Hospitals in Geneva, Lausanne, Berne, Zurich and Basel and the Cantonal Hospitals of St Gallen and Lugano, providing that these centers and affiliated Ethics Committee do accept to enrol patients in the present study. The patients will be recruited during their routine visits to the sites by the local investigators. The use of recruitment advertisements or flyers is not intended.*

## 9 Study Population

### 9.1 Inclusion Criteria

1. Provision of written, informed consent
2. Age >30 years
3. Moderate coronary heart Disease (CHD) risk, defined as FRS of 10-15%
4. HIV positive
5. Stable ARV regimen > 3 months (i.e. no recent drug change [changes in dosages are accepted])
6. Plasma HIV viral load <200copies/ml for  $\geq$  6 months

### 9.2 Exclusion criteria

1. Recommended use of lipid lowering drug therapy according to Australian Guidelines (National heart foundation 2012)
2. Family History of myocardial infarction or stroke in a male first degree relative before 55 years of age, or a female first degree relative before 65 years of age
3. Type 2 Diabetes
4. Familial hypercholesterolemia
5. Aboriginal or Torres Strait Islander people with LDL-C >2.5 mmol/L
6. Blood pressure  $\geq$  180/110
7. Documented history of:
  - a. Ischemic stroke or transient ischemic attack (TIA)
  - b. Peripheral arterial disease (regardless of severity)
  - c. Congestive heart failure
  - d. Coronary artery disease or ECG findings consistent with prior MI
8. Carotid artery stenosis or >50% occlusion of the carotid artery known previously or discovered during screening procedures
9. Total Cholesterol > 7.5 mmol/L
10. Triglyceride level >4.0 mmol/L
11. HDL-c <1 and Total cholesterol > 6.5mmol/L
12. Current or prior (last 6 months) statin therapy

13. Current or prior (last 6 months) use of ezetimibe
14. Current or prior (last 6 months) use of fibrates or niacin
15. Contraindication to statin use
  - a. Pregnancy or lactation
  - b. Hypersensitivity to statins
  - c. Known myopathy or baseline CK > 3x ULN
  - d. Contraindicated concurrent medication
  - e. Current cyclosporine, fusidic acid or oral corticosteroid use
16. Concomitant antiplatelet drug (Aspirin, Abciximab, Anagrelide, Cilostazol, Clopidogrel, Dipyridamole, Eptifibatide, Ticagrelor, Ticlopidine, Tirofiban, Terutroban)
17. Unable to complete study procedures (i.e. attendance at AH for cIMT and cPWV testing or cIMT images not accepted for analysis despite redo examination)
18. Any active, clinically significant disease (including but not limited to; pancreatitis, significant psychiatric disorders, acquired immunodeficiency syndrome (AIDS) defining illnesses) which may impact on the results of the study, increase the risk of serious adverse events (SAE) or limit participants life expectancy to < 24 months
19. Concomitant renal or hepatic disease, defined as the presence of the following:
  - a. Creatinine clearance <50 ml/min (calculated using the Cockcroft-Gault equation)
  - b. Transaminase (ALT, AST) above 3 times upper normal limit
  - c. Acute hepatic failure
  - d. Compensated cirrhosis Child Class B or C

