## 5 Flow Chart

Assessment	Screen	Baseline	Post randomization				
Week	-4	0	12	24	48	72	96
Written Informed consent	X						
Inclusion / exclusion criteria	X						
Demographic questionnaire a	X						
Physical examination b	X	X			X		X
Compliance assessment c					X		X
Weight & Height measurement d	X				X		X
Adverse event assessment e		X	X	X	X	X	X
Risk Score Calculation f	X						
Laboratory Assessments							
T Cells	X		X	X	X	X	X
HIV RNA viral load	X		X	X	X	X	X
FBE g	X	X	X	X	X	X	X
Biochemistry h	X	X	X	X	X	X	X
Fasting Lipids/glucose i	X	X		X	X		X
hsCRP		X	X				X
Research Blood samples j		X	X		X		X
Structural assessments							
Carotid IMT k	X				X		X
Pulse Wave Velocity l	X				X		X

a Demographic data, medical history and medication questionnaire (will be performed with a trained interpreter if required)

b Includes blood pressure measurement, cardiovascular examination; electrocardiogram (ECG) at screening visit only

c See appendix 17.2: Compliance self-assessment questionnaire and visual analogue scale

d Height will only be measured at screening visit. Body Mass Index (BMI) will be calculated at screening and 12 and 24 month post randomisation

e Unscheduled visits may be performed for safety/tolerability concerns

f Framingham (FRS) and Data Collection on Adverse Events of Anti-HIV Drugs (D.A.D) risk scores calculated

g Full Blood Examination: Haemoglobin, White cell count, Lymphocyte count, Neutrophil count, Platelet count

h Including sodium, potassium, bicarbonate, chloride, calcium, phosphate, urea, creatinine; Liver function tests (LFTs): alanine aminotransferase (ALT), alkaline phosphatase (ALP), total protein, albumin; creatinine phosphokinase (CPK), pregnancy screen in women with child bearing potential

i Participants will fast overnight and have bloods taken in the morning for total cholesterol (TC), low-density lipoprotein cholesterol (LDL), high-density lipoprotein cholesterol (HDL), triglycerides (TG) and glucose

j Blood for markers of innate immunity and inflammation; see Section 11.2 for full description of testing to be performed and stored bloods for future projects

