### 9.4 Removal of participants from therapy/assessment

Participants will be withdrawn from the trial if:

1. A SAE occurs which is thought to be related to involvement in the study
2. The subject withdraws consent
3. The subject becomes pregnant
4. The subject is diagnosed with clinical cardiovascular disease
  - a. Cardiovascular
    - i. Acute myocardial infarction (AMI)
    - ii. Development of angina
    - iii. New ECG changes consistent with cardiovascular disease
  - b. Cerebrovascular
    - i. Stroke or Transient Ischaemic Attack (TIA)
  - c. Peripheral vascular disease
    - i. Symptomatic claudication
5. The subject is diagnosed with an acute serious medical illness that would be a contraindication to statin therapy i.e.
  - a. Acute viral hepatitis ( A, B or C)
6. CK or transaminase elevation (> 3 times)

7. Subject is judged by the investigator to be at significant risk of failing to comply with the provisions of the protocol so as to cause harm to self or seriously interfere with the validity of the study result.

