### **Laboratory assessments for safety**

Routine laboratory assessments for safety and tolerability will be performed including:

- Full Blood Examination (FBE)
  - o Consisting of; Haemoglobin (Hb), total White Cell Count (WCC), Lymphocyte Count (Lymp), Neutrophil Count (Neut) and Platelet count (Plt)
- Biochemistry
  - o Consisting of; Sodium (Na), Potassium (K+), Chloride (Cl), Bicarbonate (HCO3), Calcium (Ca), Phosphate (PO4), Urea (Ur), Creatinine (Cr) and creatinine phosphokinase (CPK)

- An estimated glomerular filtration rate (eGFR) based on the Modification of Diet in Renal Disease (MDRD) equation is calculated electronically by the AH laboratory and will be recorded
- Liver Function Tests: Total Protein (TP), Albumin (Alb), Bilirubin (Bil), Alanine aminotransferase (ALT), Alkaline phosphatase (ALP) and Gamma-glutamyl transpeptidase (GGT)
- Pregnancy screen in women with child bearing potential (at screening visit); Beta Human chorionic gonadotrophin ( $\beta$ -HCG)

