#### Assessments

1. Demographic data, medical history and medication questionnaire to be completed
2. Full physical examination including:
  - a. Height and weight
  - b. Assessment of peripheral pulses
  - c. Blood pressure
  - d. ECG
3. Laboratory assessments
  - a. FBE and biochemistry
  - b. Beta HCG for all women of child bearing potential
  - c. Fasting metabolic assessment
  - d. HIV viral load and CD4+ T cell count (and percentage)
4. Structural assessments
  - a. cIMT
  - b. cPWV (\*Melbourne Participants only)
5. Calculations
  - a. BMI

- b. Creatinine clearance
- c. FRS
- d. D.A.D. risk score

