Current or prior (last 6 months) statin therapy		 YES	 NO
Current or prior (last 6 months) use of ezetimibe		 YES	 NO
Current or prior (last 6 months) use of fibrates or niacin		 YES	 NO
Pregnancy or lactation		 YES	 NO
Hypersensitivity to statins		 YES	 NO
Known myopathy or baseline CK > 3x ULN		 YES	 NO
Contraindicated concurrent medication (to statin use)		 YES	 NO
Current cyclosporine, fusidic acid or oral corticosteroid use		 YES	 NO
Concomitant antiplatelet drug		 YES	 NO
Unable to complete study procedures (i.e. attendance at AH for cIMT and cPWV testing or cIMT images not accepted for analysis despite redo examination)		 YES	 NO
Concomitant renal or hepatic disease, defined as the presence of the following:		 YES	 NO
    Creatinine clearance <30 ml/min [CCL = _____ ]		 YES	 NO
    Transaminases (ALT, AST) >3x the upper limit of normal		 YES	 NO
    Acute hepatic failure		 YES	 NO
    Compensated cirrhosis Child Class B or C		 YES	 NO
Other active significant disease		 YES	 NO
- Describe	_____		
Eligible for Trial?		 YES	 NO

Completed by: \_\_\_\_\_

Signed \_\_\_\_\_

Date / /

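### The AST part of the transaminase exclusion has no AST test or reference range in the protocol, and the cirrhosis exclusion leaves decompensated disease unnamed

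*Combined protocol and SAP*

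**What the plan says.** The renal and hepatic exclusion appears four times: in the synopsis (item 17), section 9.2 (item 19), section 12.3 (item 26) and the Inclusion/Exclusion Checklist in appendix 22.1.1.

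- **Transaminases.** Section 9.2 reads "Transaminase (ALT, AST) above 3 times upper normal limit". The checklist line begins "Transaminases (ALT, AST" and carries the same threefold limit.
- **Cirrhosis.** All four copies read "Compensated cirrhosis Child Class B or C". Acute hepatic failure is a separate item, 19c.

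The tests meant to supply the results are specified elsewhere. Section 12.1 orders "FBE and biochemistry" at screening, without further detail. Section 11.2 gives "Liver Function Tests: Total Protein (TP), Albumin (Alb), Bilirubin (Bil), Alanine aminotransferase (ALT), Alkaline phosphatase (ALP) and Gamma-glutamyl transpeptidase (GGT". Footnote h of the flow chart gives "Liver function tests (LFTs): alanine aminotransferase (ALT), alkaline phosphatase (ALP), total protein, albumin". Section 11.2 also says that local laboratory ranges apply and points to appendices 22.3 and 22.4.

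Section 12.3 closes by requiring every eligibility criterion to be met before a baseline visit is booked. The checklist is signed.

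**The concern.** A threshold criterion needs a measured value and an upper limit of normal. For AST the protocol specifies neither, yet sites must sign that the criterion has been checked. A candidate whose AST is above the limit while ALT is below it would pass on the specified tests.

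The cirrhosis item has a different difficulty. It restricts the exclusion to compensated disease and then attaches Child classes B and C. Sites in two countries may read this differently, and no copy of the criteria settles it.

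These items form the hepatic safety screen for a drug whose side effects, as listed in section 10.8, include transaminase elevation, jaundice and hepatitis. What is at stake is consistent application of a safety exclusion. The efficacy analysis is not affected.

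**Working it through.** No formula applies, and the plan gives no figure to reproduce. The check sets each statement of the criterion beside each list of tests and limits.

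**AST against ALT**

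| Place | ALT | AST |
|---|---|---|
| Synopsis, exclusion 17b | named | named |
| Section 9.2, item 19b | named | named |
| Section 12.3, item 26b | named | named |
| Checklist, appendix 22.1.1 | named | named |
| Flow chart, footnote h | listed | absent |
| Section 11.2, liver tests | listed | absent |
| Appendix 22.3 (Melbourne ranges) | 12-52 U/L | absent |
| Appendix 22.4 (Swiss ranges) | M 12-50, F 9-42 U/L | absent |

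AST is thus in 4 of 4 statements of the criterion, 0 of 2 test lists and 0 of 2 reference-range tables. ALT is in 4 of 4, 2 of 2 and 2 of 2. The abbreviation list defines ALT but not AST. AST otherwise appears only in the severity-grading table of appendix 22.6. That table also grades parameters absent from the trial's panels, such as INR, lipase and troponin, so it does not schedule a test.

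Therefore ALT above three times the upper limit can be determined at every site, while AST above three times the upper limit cannot be determined from the specified panels and ranges.

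**Cirrhosis**

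1. The wording is identical in all four copies, so none corrects another.
2. Decompensated cirrhosis is named in 0 of the 4.
3. The neighbouring items do not name it: 19a is renal, 19b is a transaminase limit and 19c covers acute failure only.
4. The list of contraindications to statins (item 15) names no liver condition.
5. What remains is item 18, any active and clinically significant disease, which the investigator judges.

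Steps 1 to 5 need nothing from outside the documents. The further statement that the qualifier conflicts with the classes assumes ordinary usage, in which compensated cirrhosis corresponds to class A. The protocol does not define the classes.

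**Creatinine clearance, same item**

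The synopsis, section 9.2 and section 12.3 exclude below 50 ml/min. The checklist excludes below 30 ml/min. A candidate between 30 and 50 ml/min is excluded by the protocol text and not by the checklist.

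**The case against.** The best defence is that the criteria still function. ALT is measured at screening and has an upper limit in both countries, so 19b operates through ALT. That stands: a reader might infer that the exclusion cannot work, and the documents do not support this.

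It can also be said that the test lists are not closed. Footnote h opens with an inclusive word and omits bilirubin and GGT, which section 11.2 lists. Section 11.2 introduces its safety tests in a similarly open way. Candidates come from HIV clinics and cohort visits, where routine care may supply further results. This too stands in part: the documents show that AST is in no specified panel, not that it is never tested. It does not remove the mismatch, because nothing tells a site to obtain AST and neither range table has a row for it.

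A reader might extend the AST gap to the withdrawal rule in section 9.4, item 6, "CK or transaminase elevation (> 3 times". That does not follow. The rule names no particular enzyme, and ALT is a transaminase on the panel.

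On cirrhosis, item 18 is a real exclusion with its own checklist line, and screening includes history, physical examination, bilirubin and albumin. Section 10.8 lists transaminase elevations as rare, and jaundice and hepatitis as very rare. These points narrow the gap. They do not settle the wording, because the outcome still depends on each investigator's judgement. A reader might also infer that 19d describes a nearly empty group. That would need a definition of the classes and figures that the documents do not give.

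**Conclusion.** The point holds in a limited form. The AST part of 19b cannot be applied from the trial's specified tests and ranges; the ALT part can. Item 19d is unclear in all four copies, and decompensated cirrhosis is left to item 18. The AST finding and the omission of decompensated cirrhosis rest on the text alone. The internal conflict in 19d rests on the ordinary meaning of the Child classes, which is an assumption.

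The number of candidates affected cannot be derived. Neither mismatch changes the planned 102 participants, the power or the alpha. It merits correction because it concerns a stated safety exclusion and costs almost nothing to put right.

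**What to change.** 1. Make the AST criterion agree with the laboratory specification. Either add AST to the liver tests in footnote h and section 11.2 and to the ranges in appendices 22.3 and 22.4, or remove it from all four copies of the criterion.
2. Have the sponsor reconcile the cirrhosis wording in the synopsis, section 9.2, section 12.3 and the checklist, so that the qualifier and the classes agree and the text states whether decompensated cirrhosis is excluded. Which rule applies is a clinical decision for the sponsor.
3. In the same revision, reconcile the creatinine clearance limit between the three protocol statements and the checklist.

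The cost is protocol and checklist wording and, if AST is kept, one more analyte in biochemistry that is already scheduled.

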### 9.3 Prohibitions

Concurrent participation in non-related clinical trials is allowed as long as there is no impact on the objectives of this trial.

### 9.4 Removal of participants from therapy/assessment

Participants will be withdrawn from the trial if:

1. A SAE occurs which is thought to be related to involvement in the study
2. The subject withdraws consent
3. The subject becomes pregnant
4. The subject is diagnosed with clinical cardiovascular disease
  - a. Cardiovascular
    - i. Acute myocardial infarction (AMI)
    - ii. Development of angina
    - iii. New ECG changes consistent with cardiovascular disease
  - b. Cerebrovascular
    - i. Stroke or Transient Ischaemic Attack (TIA)
  - c. Peripheral vascular disease
    - i. Symptomatic claudication
5. The subject is diagnosed with an acute serious medical illness that would be a contraindication to statin therapy i.e.
  - a. Acute viral hepatitis ( A, B or C)
6. CK or transaminase elevation (> 3 times)

7. Subject is judged by the investigator to be at significant risk of failing to comply with the provisions of the protocol so as to cause harm to self or seriously interfere with the validity of the study result.

### 9.5 Pregnancy

Women of child-bearing potential will be screened for pregnancy on admission to the study. Due to a lack of study data relating to the effects of statins on pregnant woman and/or the foetus those who are found to be pregnant will be excluded from study participation and referred to an appropriate medical service.

Female participants will be advised to avoid pregnancy while participating in the study. Women who become pregnant after randomisation will be withdrawn from the trial but will continue to be monitored for the development of adverse events (AE) or serious adverse events (SAE).

*For Switzerland: Women of childbearing potential must use two reliable contraceptive methods during the entire trial, from day 1 to one month after the end of the trial. Accepted methods are hormonal methods such as the birth control pill associated with a barrier method such as the preservative.*

## 10 Study Medication

Participants will be randomly assigned in a 1:1 ratio to receive rosuvastatin or matched placebo.

### 10.1 Rosuvastatin

Rosuvastatin is a hypolipidaemic agent and member of the drug class of statins used to treat high cholesterol and related conditions. Rosuvastatin is licensed by the Australian Therapeutic Goods Administration (TGA) for the prevention of major cardiovascular events and in patients with hypercholesterolemia (including familial hypercholesterolemia). Rosuvastatin should be used as an adjunct to dietary modification.

Rosuvastatin capsules of 10mg and 20mg dosages will be purchased from the manufacturer - Astra Zeneca.

